2 BACKGROUND

Chemotherapy-induced peripheral neuropathy (CIPN) is one of the most common and disabling complications of cancer chemotherapy. CIPN is a major cause of morbidity and reduced quality of life among cancer survivors due to pain, gait instability, and fall related injury. Up to 60% of patients receiving potentially neurotoxic chemotherapeutics develop CIPN, 40% of whom have persistent neuropathy after termination of chemotherapy.^{2,3} CIPN commonly necessitates dose reduction or cessation of therapy, potentially limiting treatment efficacy and likely impacting patient outcomes.⁴ First-line treatments include anticonvulsants, tricyclic antidepressants, selective serotonin and norepinephrine reuptake inhibitors (SSNRIs) and topical lidocaine.⁵

Second-line treatments include opioids. Given the risk of abuse, overdose and addiction, treatments besides opioids are advised and warrant investigation. A multimodal approach may be most effective, with acupuncture being a safe option reporting low rates of adverse events⁶. Acupuncture treatment (AT) is a well-tolerated and safe treatment option frequently used for symptoms associated with cancer therapies such as nausea, vomiting, xerostomia and fatigue.⁷ Several case series and small uncontrolled trials of AT for CIPN suggest potential efficacy, although well-designed and powered clinical trials are lacking and mechanisms underlying AT's potential efficacy are unknown.⁸⁻¹⁴

Although drug-induced damage to the peripheral nervous system is well recognized in CIPN, the central nervous system (CNS) also shows concomitant involvement. Much of our current understanding of the pathophysiology of central pain processing in chronic painful conditions such as diabetic neuropathy, trigeminal neuralgia, post-herpetic neuralgia and chronic low back pain has utilized functional magnetic resonance imaging (fMRI). Previous pain-related functional studies identified alterations in brain activation in multiple cortical and subcortical regions including the frontal lobe, insular cortex, somatosensory cortex, thalamus, periaqueductal grey and precuneus.¹⁵

While fMRI has not yet been used to evaluate mechanisms of action of AT in the context of CIPN, an increasing number of studies have applied fMRI to investigate AT over a wide range of pain disorders. Stimulation of acupuncture points is associated with overlapping activity in cortical and subcortical brain regions, including the insula, thalamus, anterior cingulate cortex, primary and secondary somatosensory cortices, and deactivation in limbic-paralimbic-neocortical network. Acupuncture can modulate activity within specific brain areas, many of which are known to be important to CIPN pain processing. We hypothesize that regions involved in pain perception will show decreased connectivity between the insula, amygdala and somatosensory cortex with successful pain treatment, with decreased task-related activation of the brain's salience network (anterior cingulate and frontal insula) during mental pain imagery. ¹³⁻¹⁵

Additionally, neurological evidence indicates that some of the brain regions activated during pain perception are also activated when engaging in interoceptive awareness. ¹⁶ Acupuncture has been shown to alter pain processing regions but has not been evaluated regarding changes in mind-body awareness. The possible role of enhanced mind-body awareness as a mechanism of action of acupuncture has not yet been tested. This pilot study will provide a preliminary fMRI and questionnaire data for this topic. Clinical trials of interventions such as mindfulness-based cognitive therapy demonstrate increased interoceptive awareness¹⁷ and decreased depression¹⁸. It seems plausible that AT may provide an opportunity for participants to increase their mind-body awareness while they lie on the treatment table and relax, as well as via neurologic changes in the insula, amygdala, and somatosensory cortex. These regions are known to affect pain processing as well as interoceptive (or mind-body) awareness.

This pilot feasibility study aims to determine if conducting a trial of AT for CIPN is feasible at HCI. We aim to enroll and retain twenty participants who will undergo fMRI during the baseline visit, receive up to 10 sessions of AT, and undergo fMRI after completion of AT. We will examine fMRI for potential neurologic mechanisms of action of AT in CIPN management. The ultimate objective of this pilot project is to lay the foundation for a future randomized controlled clinical trial of AT for CIPN. Specifically, we will be able to demonstrate that we have the team and location in place to conduct a successful trial.

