	feasibility data will consist of calculating
	frequencies and percentages Analysis of
	questionnaires will consist of within-

group pre/post analysis with student t-test and chi square with significance will be set at .05 and two-tailed hypotheses.
Sample Size Estimation: A sample size of 25-30 participants is ideal for a pilot feasibility study ¹ . However, we are recruiting only 20 participants due to funding constraints.

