1.2 Secondary Objectives and Endpoints

To evaluate the impact of AT on the reported experience of CIPN.

- 1.2.1 To evaluate central pain processing and cortical connectivity in patients with CIPN treated by acupuncture by analyzing fMRI of all participants.
- 1.2.2 To evaluate if there is any change in patient-reported measures from before AT to after study completion.

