12 STATISTICAL CONSIDERATIONS

Data will be collected via REDCap and analyzed with SPSS. Missing data will be handled with imputation of the median value of all available data for each individual item.¹⁹

Demographics: Analysis of demographic data will consist of calculating means, standard deviations, frequencies, and proportions. Demographic information to include: age, marital status, race and ethnicity, current medications and medical history.

Feasibility data: will be analyzed by calculating frequency and percentages, specifically:

- **Recruitment** frequency count (enrollment of 20 women, average of 2 eligible women per month to participate in the trial, identification of appropriate recruitment strategies, the appropriateness of eligibility criteria),
- **Retention** frequency and percentage (70% or more participants comply with 8 or more AT sessions and complete both fMRI scans)
- Safety frequency count (zero serious adverse events directly related to AT)
- **Questionnaire completion** frequency and percentage (70% or more enrolled participants complete at least 80% of questions at all protocol-directed time points).

Questionnaires: analyses will consist of student t-test and chi square computations according to the type of data.

- CIPN-20
- CIPN-R-ODS
- BPI
- Multidimensional Assessment of Interoceptive Awareness (MAIA-2)

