Functional MRI quantification: Volume and Surface preprocessing pipelines from the Human Connectome Project will be executed for each resting sequence on completion of structural preprocessing. MultiEcho ICA Cleaning: All resting state data will additionally be processed using MultiEcho ICA pipeline (AFNI) allowing removal of non-neural components in the BOLD data. Head motion: Rigorous control of head motion begins before acquisition with subject training and instruction, continues during scanning with repeated reminders to hold still and analysis of image quality after each scan with repetition as possible, and postprocessing including voxelwise despiking, motion parameter estimation and correction, physiologic waveform regression, Multiecho ICA cleaning, and volume censoring (scrubbing). Post-hoc mean and maximal root-mean-square head motion estimates will be used as covariates for all biomarkers. Connectivity: Time series will be estimated FreeSurfer-defined subject-specific regions of interest in somatosensory cortex, anterior cingulate, anterior insula, amygdala, thalamus, medial prefrontal cortex, orbitofrontal cortex, and precuneus, as well as at 361 ROIs for graph-theoretic and network analyses (modularity and clustering coefficient) comprising 333 cortical ROIs strategically positioned at network hubs, 14 cerebellar ROIs, and 14 subcortical gray matter ROIs defined from Freesurfer segmented subject specific nuclei.

Functional MRI Analysis: We will analyze functional connectivity using a parcellation covering the cortical and subcortical gray matter at 5 mm resolution. Brain parcellation will be constructed by assessing regions of interest (ROIs) and measuring each voxel, which can represent a million brain cells. Each voxel will be tested in sequence beginning with the inferior left voxel in the cerebellum. If a voxel is greater than 5 mm distant to voxels already selected, then this voxel will be included in the set of ROI center coordinates.

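### Low-cost improvement: Section 12 analyses imaging and questionnaires separately and never relates change in connectivity, task activation or MAIA-2 to change in symptoms, although the mechanism hypothesis is about that relation

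*Combined protocol and SAP*

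**What the plan says.** The title and the Study Summary objective name mechanisms of action beside feasibility. Section 2 repeats the aim for imaging: "We will examine fMRI for potential neurologic mechanisms of action of AT in CIPN management". Its hypothesis ties the brain change to the outcome of treatment: "decreased connectivity between the insula, amygdala and somatosensory cortex with successful pain treatment". It adds that salience-network activation during pain imagery should fall. It also offers a second candidate, to be measured by MAIA-2: "The possible role of enhanced mind-body awareness as a mechanism of action of acupuncture has not yet been tested".

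The formal secondary objectives are narrower and stand apart from each other. Objective 1.2.1 is "To evaluate central pain processing and cortical connectivity in patients with CIPN treated by acupuncture by analyzing fMRI of all participants". Objective 1.2.2 is "To evaluate if there is any change in patient-reported measures from before AT to after study completion".

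For CIPN-20, CIPN-R-ODS, BPI and MAIA-2, Section 12 says that "analyses will consist of student t-test and chi square computations according to the type of data". The Study Summary gives the form of these tests, which are within participants: "group pre/post analysis with student t-test and chi square with significance will be set at .05 and two-tailed hypotheses". For imaging, Section 12 covers preprocessing, regions of interest, graph measures and a parcellation: "We will analyze functional connectivity using a parcellation covering the cortical and subcortical gray matter at 5 mm resolution". Head-motion estimates are the only covariates named there. Section 7.1 says that concurrent medications will be analysed as possible confounders, without giving a model.

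**The concern.** The hypothesis concerns a relation: connectivity falls where pain treatment succeeds. The planned analyses describe each measure by itself. A fall in mean connectivity and a fall in mean symptom score could both appear although the women whose connectivity fell were not the women who improved. In the other direction, a real link within women would go unseen if the mean of either measure barely moved. Without a control arm, mean shifts can also come from time or repeat measurement.

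What is at stake is the use of the pilot for planning. Section 2 presents it as the foundation for a randomised trial. A first estimate of the brain-symptom and awareness-symptom associations, with its uncertainty, would help to decide whether a mechanism substudy is worth carrying forward. If the associations are left to be chosen after the data are seen, the choice is wide: the 361 regions alone give 361 × 360 / 2 = 64,980 region pairs, before the several questionnaires are considered.

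**Working it through.** **Step 1. Look for a linking analysis.** The documents give no power, effect size or correlation to reproduce, and 20 is a budget figure (Section 4.3). The main check is therefore a reading of every analysis statement.

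| Part of the mechanism aim | Where stated | Analysis planned | Symptom change included? |
|---|---|---|---|
| Connectivity falls with successful treatment | Section 2 | ROI, graph and parcellation measures; motion covariates; no pre/post test named | No |
| Task activation falls | Section 2 | Task described in Section 10; no analysis in Section 12 | No |
| Mind-body awareness as mechanism | Section 2 | Pre/post test of MAIA-2 | No |
| Symptoms (CIPN-20, BPI) | Objective 1.2.2 | Pre/post test of each | Outcome only, on its own |

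There is no correlation, regression, responder contrast or mediation analysis anywhere, and treatment success is not defined. Section 15.3 (Correlative Studies) is marked not applicable. It sits beside pathology and pharmacokinetics, so I give it little weight.

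**Step 2. Can mean changes stand in for the link?** Assume a mean change of 1 SD in each of two measures, a paired t-test on each, two-sided 0.05, and 20,000 simulated trials. The 1-SD change and the correlations are my assumptions. The share of trials with both tests significant was:

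| Correlation of the changes | 20 pairs | 14 pairs |
|---|---|---|
| 0 | 97.8% | 86.9% |
| 0.7 | 98.0% | 89.0% |

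Fourteen is the retention target, 0.70 × 20. The pattern of results is almost the same whether or not the changes are linked, so the planned tests do not tell the two cases apart.

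**Step 3. What would a correlation deliver?** Using Fisher's z, the interval is tanh(atanh(r) ± 1.96 × SE). SE is 1/√(n − 3) unadjusted and 1/√(n − 4) with one covariate (change in head motion). For an assumed observed r of 0.5, atanh(0.5) = 0.549.

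| | 20 pairs | 14 pairs |
|---|---|---|
| Unadjusted SE | 1/√17 = 0.243 | 1/√11 = 0.302 |
| Unadjusted 95% CI | 0.07 to 0.77 | -0.04 to 0.81 |
| Motion-adjusted SE | 1/√16 = 0.250 | 1/√10 = 0.316 |
| Motion-adjusted 95% CI | 0.06 to 0.78 | -0.07 to 0.82 |

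The true r giving 80% power is tanh((1.96 + 0.84) × SE): 0.59 and 0.69 unadjusted, about 0.60 and 0.71 adjusted. Unadjusted power at a true r of 0.5 is 62% with 20 pairs and 45% with 14. About 30 pairs would be needed for 80%. The estimates can inform planning but cannot support a test.

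**Step 4. Are the data there?** The Section 9 calendar has CIPN-20, BPI, MAIA-2 and fMRI before treatment and at end of study. No new visit, scan or participant is needed.

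**The case against.** The strongest reply is that the plan promises less than a demonstrated mechanism. It speaks of potential mechanisms and preliminary data. Section 1 asks for changes in biomarkers, which is a pre/post question. Neither formal secondary objective asks for an association, and the conditional hypothesis appears only in the background. Its wording can also be read at group level, as connectivity after a treatment that works. All of this stands. It limits the point to an exploratory analysis that would match the plan's own hypothesis.

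A second reply is that a correlation would not establish mechanism either. In a single arm, two changes over the same interval can move together through time, medication changes or regression to the mean after selection on a CIPN-20 sensory score of at least 20. This also stands, and it sets the ceiling on what the added analyses can claim.

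A third reply is that the imaging section has a larger gap, since it names no test for pre/post change and no analysis of task activation. That is true, but filling that gap would still leave brain change and symptom change unconnected.

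Two stronger readings are tempting. A reader might infer that the imaging and questionnaire objectives fail altogether. They do not: 1.2.1 can be met descriptively and 1.2.2 by pre/post comparison. A reader might also infer that a connectivity shift is just as likely from rescanning or time as from treatment. The documents give nothing on the size of such effects, so one can say only that a shift can also arise in those ways.

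**Conclusion.** The point holds as a low-cost improvement. Followed as written, the plan never estimates the association between change in connectivity, task activation or MAIA-2 and change in symptoms, and pre/post means cannot substitute for it (97.8% against 98.0% in the 20-woman simulation). The primary feasibility endpoints, safety and sample size are untouched. The absence of a link in Section 12 is a matter of reading the text. The figures rest on assumed 1-SD changes and assumed correlations, because the documents supply none, and on 20 or 14 complete pairs. If retention falls below target, or a retained woman lacks a questionnaire, precision is worse than shown.

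**What to change.** Add to Section 12 a short list of pre-specified exploratory associations of change from before treatment to end of study:

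1. One summary of the hypothesised connectivity (for example, the mean Fisher-z across the insula, amygdala and somatosensory region pairs) against change in CIPN-20 sensory score, adjusted for change in mean head motion. Do the same for one summary of salience-network task activation.
2. One MAIA-2 summary, named in advance, against the same symptom change. The plan defines no summary of its 37 items, so the choice must be written down.
3. BPI pain severity as a supporting symptom measure only. Section 5.1.4 admits women with altered sensation and no pain, who may have no room to improve on BPI.

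Report each as a correlation with a 95% confidence interval and no significance threshold. At this size, a threshold would often discard a real link. State that a pre/post mean change alone will not be reported as evidence of mechanism. State also that, in a single arm, these associations generate hypotheses and cannot be attributed to acupuncture.

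The cost is a few extra, imprecise estimates from data already collected and a more cautious statement about mechanism.

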3 DRUG INFORMATION

N/A

4 STUDY DESIGN

4.1 **Description**

We propose a pilot feasibility trial. Oncologists at Huntsman Cancer Institute (HCI) will be informed of the trial and asked to refer female patients diagnosed with breast or gynecologic cancer and CIPN who have completed all paclitaxel or docetaxel treatments three or more months previously. All referred patients will be informed of the study and voluntarily recruited by the Study Coordinator (SC). The SC will call the individual after sending a recruitment letter, inform them of the study, screen them for eligibility, and if consent is obtained, enroll the participant. Standard oncological care is defined as care the participant was already receiving and that care will not be interrupted in any way for any study participant.

4.2 **Dose Limiting Toxicity**

N/A

4.3 Number of Patients

Twenty participants will be enrolled. Sample size for this pilot feasibility study is determined by budgetary constraints. While a sample of 25-30 would be ideal for the aims of this study¹, we are limited by our study budget to twenty participants.

4.4 Number of Study Centers

All participants will be recruited from HCI and AT will be delivered onsite at HCI in the Linda B. and Robert B. Wiggins Wellness and Integrative Health Center. This is a single-center pilot phase II trial.

4.5 Study Duration

Eighteen months.

5 ELIGIBILITY CRITERIA

This eligibility checklist is used to determine patient eligibility and filed with signature in the patient research chart.

Patient No.	
Patient's Initials:	(L,F,M)

5.1 Inclusion Criteria Yes/No (Response of "no" = patient ineligible)

- 5.1.1 _____ Female age 18 or older.
- 5.1.2 Histologically proven breast, uterine, cervical or ovarian cancer of any stage.
- 5.1.3 Received either (1) a Paclitaxel treatment dose of at least 480 mg/m² paclitaxel as a single or combination agent or (2) a Docetaxel treatment dose of at least 150 mg/m² docetaxel as a single or combination agent. Treatment must be completed at least 3 months prior to enrollment.
- 5.1.4 Eligible patients report at least 1 month of altered sensation and/or pain in the feet (with or without presence in one or both hands) with a score of greater than or equal to 20 for CIPN on the sensory subscale of the CIPN-20 (scale 0-100).

5.1.5. _____ Able to provide informed consent and willing to sign an approved consent form that conforms to federal and institutional guidelines.

5.1.6. ECOG status of 0 (asymptomatic), 1 (symptomatic but completely ambulatory) or 2 (symptomatic, <50% in bed during the day).

5.2 Exclusion Criteria Yes/No (Response of "yes" = patient ineligible)

- 5.2.1 Preexisting neuropathy due to other identified etiologies includes diabetes, vitamin B12 deficiency, or alcoholism.
- 5.2.2 Having received more than 6 acupuncture treatments for any condition in the last six months.
- 5.2.3 Patients with claustrophobia, pacemakers, non-MRI compatible breast expanders or port-a-caths, neurostimulator devices, current or expected pregnancy, exposure to shrapnel, left-handedness, recent tattoos or otherwise unsafe for MRI scanning.

I certify that this patient meets all inclusion and exclusion criteria for enrollment onto this study.

Investigator Signature

Date

6 STRATIFICATION FACTORS N/A

7 TREATMENT PLAN

7.1 Administration Schedule

Twenty participants will be enrolled. The manualized acupuncture treatment (AT) intervention will be designed by [name] and [name] and administered by [name] and members of Huntsman acupuncture team. Ten sessions of AT will be delivered: twice per week for 2 weeks, thereafter once per week for six weeks, with a total of 10 treatments during a two-month course. Each session will last 45-60 minutes, with acupuncture needles retained 30-40 minutes. A minimum of 8 treatments must be received within the acupuncture treatment window. Concurrent medications are allowed as prescribed and will be tracked in the study and analyzed as potential confounders.

Participants in the study will undergo study interview and fMRI at the following two time points: within 9 days after baseline following enrollment and within one week of acupuncture treatment completion. Clinical data including current medications and medical history and fall rates will be gathered during the baseline and study conclusion. Questionnaires will be completed in person or emailed to patients via REDCap at baseline and study conclusion, as well as at a 3-month follow-up. Reminder calls and AT appointments will be scheduled by HCI Wellness and Integrative Health Center personnel in coordination with the study coordinator (SC). The SC will aid participants in scheduling fMRI with an online scheduling system.

7.2 Acupuncture treatment and ongoing standard care Treatment

7.2.1 How Supplied, Stored, Packaged and Labeled

Acupuncture needles arrive labeled, sealed and boxed from the manufacturer and are stored in a secured cabinet. All acupuncture needles remain unopened until use.

7.2.2 Preparation and Administration

Acupuncture will be provided according to standard procedure and will include use of Clean Needle Technique.

Clean Needle Technique

In the United States, Clean Needle Technique (CNT) is governed by the CCAOM, the Council of Colleges of Acupuncture and Oriental Medicine. This study will follow the CNT outlined by the CCAOM, 6th ed. (2009) CNT helps to ensure participant and practitioner safety in the acupuncture process

General CNT Guidelines

Clean needle technique requires the following: Hand washing before and after patient contact, and before setting up a clean field Set up a clean field with equipment and supplies Locate the acupuncture point Uni-directional swabbing of the acupuncture point with alcohol Needling with guide tube and adjust needle to desired depth At end of session, remove and immediately isolate acupuncture needles into approved sharps containers

Acupuncture Needles

Acupuncture needles are regulated as medical devices by the United States Food and Drug Administration. The acupuncture needles to be used in this clinical trial will be single-use, sterile acupuncture needles.

Acupuncture Needles: DBC[™] Spring Ten needle .16 x 30mm, 40-gauge (manufactured by DBC Made in Korea; distributed by Lhasa OMS, Inc. Weymouth, MA) Auricular Acupuncture Needles: DBC[™] Sooji Chim Korean Hand Needles .18x30mm, 42-gauge DBC needles (manufactured by DBC Made in Korea; distributed by Lhasa OMS, Inc. Weymouth, MA) Scalp Acupuncture Needles: Nano Tech[™].16 x 30mm, 40-gauge (manufactured by DBC Made in Korea; distributed by DBC Made in Korea; distributed by Lhasa OMS, Inc. Weymouth, MA)

Note: if these specific needles are unavailable for use, whichever brand is used clinically by the staff will also be used for study participants.

The acupuncture protocol and procedures employed have been devised with adherence to the Standards for Reporting of Controlled Trials in Acupuncture (STRICTA) recommendations. The point prescription in this study is a manualized protocol (i.e., a protocol that is standardized but allows the Study Acupuncturist to modify treatments based on the patient's current symptoms).

Manualized Protocol

A manualized protocol was chosen, as opposed to a fixed acupuncture point protocol, in order to facilitate a standardization of treatments and because it was shown to be effective in a number of other acupuncture clinical trials. Acupuncture points relevant to an individual patient will be selected from the list below.

ACUPUNCTURE POINTS ALLOWED IN THE MANUALIZED PROTOCOL

Point	Location – from Chinese Acupuncture and Moxibustion, Foreign Languages
Name	Press, Beijing (2010, Xinnong, C., 3rd ed.)
Full bo	dy acupuncture points (given at each visit, bilaterally)
LI 10	On the line joining Yangxi (LI-5) and Quchi (LI-11), 2 cun below the cubital
	crease.
GB	Anterior and inferior to the external malleolus, in the depression on the lateral
40	side of the tendon of m. extensor digitorum longus.
GB	In the depression anterior and inferior to the head of the fibula.
34	

ST	On the dorsum of the foot, at the midpoint of the transverse crease of the ankle
41	joint, in the depression between the tendons of m. extensor digitorum longus and
	hallucis longus, approximately at the level of the tip of the external malleolus.
ST	3 cun below Dubi (ST-35), one finger-breadth (middle finger) from the anterior
36	border of the tibia.
KD 3	In the depression between the tip of the external malleolus and the anterior side
	of the tendon Achilles.
Ba	When the hand is made into a fist, six of these points lie in the depressions
Xie	between the metacarpal heads, proximal to the web margins. The remaining two
	points lie equidistant between the thumb and index metacarpals, proximal to the
	web margins.
Ba	On the dorsum of the foot, between the toes, 0.5 cun proximal to the margin of
Feng	the web.
Auricu	lar acupuncture points: Shen Men. Thalamus, Endocrine, Point Zero, Sympathetic

Standard care will be delivered according to the participants' healthcare team.

